#### **C. Study Population**

- Patients with diagnosis of chronic migraine receiving FDA-approved treatment with BoNTA injection as per standard protocol used in PREEMPT study [2]. Standard protocol consists of 31 injection sites, with total dose ranging from 155 u to 195u.
- Exclusion criteria:
  1. Age < 18, or > 79
  2. Subjects whom BoNTA injections deviate from standard protocol for any reason, such as head/neck infection, head deformity, recent surgery...etc.
- Study population will be randomized into two groups; preserved saline and preservative-free saline

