#### **B. Study Materials**

Our preservative-free saline is a 0.9% sodium chloride injection. Each milliliter contained 9 mg of sodium chloride. The solution is supplied in 25-mL, single-dose vials.

Our preservative-containing saline is a bacteriostatic 0.9% sodium chloride injection. Each milliliter contained 9 mg of sodium chloride and 9 mg of benzyl alcohol added as a bacteriostatic preservative. The solution is also supplied in 25-mL, single-dose vials.

Both preserved saline and preservative-free saline are identical-appearing, colorless solutions.

BoNTA (Botox® Allergan Inc) is a powder vial containing 200 u. Powder is reconstituted with 4 ml of normal saline and then drawn in four 1 ml syringes. All four syringes are used in a single patient in one session.

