#### D. Study Procedures

UHCC headache clinic performs 20-25 BoNTA injections a week on average. Enrollment plan is as following: on weekly basis, one of the investigators, either SH or AF, will contact all patients scheduled for BoNTA injections and explain the study's objectives and details. If the subject agrees to enroll, he/she will be assigned a study serial number and will be randomized to one of the two groups. Randomization will be done through a simulated "coin flipper" website; [www.random.org](http://www.random.org). Heads will be assigned to the preserved saline group, and tails will be assigned to the preservative-free saline group. SH and AF will keep the assignment sheet in a password-protected excel file that only they have access to.

On the day of the procedure, informed consent will be confirmed and signed. Then, each subject will receive 10-15 minute session on the appropriate use of headache diary.

Same randomizing investigator will reconstitute BoNTA vial (Allergan Inc) using one of the two identical solutions, and then hand it to the principal investigators; AZ or LM, who will be

performing the procedure using 30G 1/2' needles. AZ ,LM, and the subject will all be blinded to which solution is used for reconstitution.

Following the injections, subjects will be asked to rate procedure-related pain using verbal pain rating scale (0 to 10). They will be asked to maintain a 7-day headache diary (see supplementary). Prepaid mail envelopes will be provided to ensure the return of the diaries following their completion.

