#### **VI. ETHICAL CONSIDERATIONS**

##### **A. Informed Consent**

Informed consent will be obtained by investigators SH or AF at the time of the visit. Refusal of participation will not affect the treatment plan, and the subject will continue to receive BoNTA injections as scheduled, using the standard preservative-free saline.

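### Minor safety improvement: the exclusion list does not cover a patient who reports a previous reaction to benzyl alcohol, the one ingredient the trial adds to this clinic's standard diluent

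*Combined protocol and SAP*

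**What the plan says.** Section III.C (Study Population) excludes patients younger than 18 or older than 79. It also excludes "Subjects whom BoNTA injections deviate from standard protocol for any reason, such as head/neck infection, head deformity, recent surgery...etc". On what counts as standard it says: "Standard protocol consists of 31 injection sites, with total dose ranging from 155 u to 195u". The description names no diluent.

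Section III.B (Study Materials) describes two salines with the same sodium chloride content. Of the preserved one it says: "Each milliliter contained 9 mg of sodium chloride and 9 mg of benzyl alcohol added as a bacteriostatic preservative". A 200 u vial is made up in 4 ml, and all four 1 ml syringes go to one patient in one session.

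Section VI.A (Informed Consent) gives the clinic's usual practice. If a patient declines, "the subject will continue to receive BoNTA injections as scheduled, using the standard preservative-free saline".

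Section III.D (Study Procedures) has an investigator contact scheduled patients each week and explain the study. Then: "If the subject agrees to enroll, he/she will be assigned a study serial number and will be randomized to one of the two groups". The investigator who randomizes also reconstitutes the vial. The two injectors "and the subject will all be blinded to which solution is used for reconstitution".

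Section VI.B (Risks and Side Effects) states that neither saline has known risks or side effects. Section IV (Data Collection) lists no allergy history among the data collected.

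**The concern.** The trial deliberately gives about half its subjects an ingredient that this clinic does not otherwise use. Eligibility for routine BoNTA treatment here does not depend on whether a patient tolerates that ingredient, so routine care supplies no screen that the trial can lean on. The protocol's own list does not supply one either.

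At stake is a single, narrow situation: a patient already reports a previous reaction to benzyl alcohol, is eligible as written, and is allocated by coin toss to receive it. If the history is asked for before the toss, that patient is not randomized and the place goes to someone else. This is a point about patient safety and orderly eligibility, not about inference.

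**Working it through.** **1. Does either exclusion reach such a patient?** The age limits do not. The second exclusion depends on the injections deviating from standard protocol. Section III.C describes that protocol as 31 sites and 155 to 195 u. A patient with this history can receive all 31 sites at the usual dose, so nothing deviates. The exclusion is open-ended as to the reason for a deviation, but there must be a deviation first. Its examples (infection, deformity, surgery) all concern whether the injections can be given in the usual way. Neither exclusion applies.

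**2. Is the exposure added by the trial?** Inputs from Section III.B: 200 u in 4 ml; 9 mg/ml benzyl alcohol. Doses from Section III.C: 155 to 195 u.

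- Concentration: 200 / 4 = 50 u/ml.
- Lowest dose: 155 / 50 = 3.1 ml; 3.1 × 9 = 27.9 mg.
- Highest dose: 195 / 50 = 3.9 ml; 3.9 × 9 = 35.1 mg.
- All four syringes emptied: 4 × 9 = 36 mg.

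So a subject in the preserved-saline group receives about 28 to 36 mg per session. The comparison group and the clinic's standard practice (Section VI.A) receive 0 mg. These are amounts of exposure, not of harm.

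**3. Does a written step catch it before allocation?** Section III.D goes from agreement to serial number to coin toss, with no question about previous reactions. Section IV does not collect the history.

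**4. Does the point touch the sample size?** The plan's figure reproduces. Inputs from Section V (Data Analysis): difference 1.5, SD 1.9, alpha 0.05 (taken as two-sided, which the section does not state), power 90%. The normal approximation is n per group = 2 × (1.960 + 1.282)² × (1.9 / 1.5)² = 33.7, so 34. The t-distribution version gives 34.7, so 35 per group and 70 in total, with power 90.2%. An exclusion applied before randomization leaves 35 + 35 in place. Even if one such subject were instead lost after the toss (34 + 35), power would be 89.8%.

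**5. How many patients?** The documents give no rate of previous reaction, so the number affected cannot be computed from them.

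**The case against.** The strongest reply is that the documents report no hazard. Section VI.B says there are no known risks from either solution, and Section I says that preserved saline is in common use among practitioners. That stands: nothing in the protocol shows that benzyl alcohol harms patients in general. A general statement about a product does not, however, settle what to do with an individual who reports an exception.

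The second reply is that safeguards already exist. Before any toss, an investigator explains the study, whose whole subject is preserved against preservative-free saline. A patient who knows of a previous reaction may say so, or may decline and keep the usual diluent. Subjects also come from the injectors' own practices, so they are not strangers to them. This stands in good part and is why the residual risk is small. What it leaves is reliance on the patient to raise the matter unprompted.

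A reader might infer from the double-blind label that nobody present could prevent the exposure. The documents do not support that. Only the injectors and the subject are blinded. The investigator who randomizes also makes up the vial, knows the solution, and could withhold it if the history came to light.

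A reader might also infer a material probability that some subject is harmed or wrongly exposed. Any such figure would rest wholly on an assumed reaction rate and would describe allocation, not harm.

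**Conclusion.** The point holds as a cheap, minor safety improvement. As written, a patient who reports a previous reaction to benzyl alcohol is eligible and can be allocated to about 28 to 36 mg of it per session, against none under the clinic's standard diluent. No written question stands between agreement and the coin toss.

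Its size is small and cannot be put as a number of patients. The conclusion rests on two readings of the text: that standard protocol in Section III.C means sites and dose, and that preservative-free saline is this clinic's usual diluent, as Section VI.A says. It assumes no general hazard. The endpoint, planned 70 subjects, power and analysis are unaffected. The documents do not support reading this as a flaw in the trial's validity or as evidence that preserved saline is unsafe.

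**What to change.** Add one line to the exclusions in Section III.C: *known hypersensitivity or previous reaction to benzyl alcohol or preserved saline*. Ask the question at the weekly contact in Section III.D, before the serial number is given and the coin is tossed.

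The cost is one line of text and one question in a conversation already planned, with no extra staff, visit or procedure. The only downside is that a rare patient is excluded. That patient is replaced before randomization from a clinic which, by its own account, is busy enough: "UHCC headache clinic performs 20-25 BoNTA injections a week on average". The sample size calculation needs no change.

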#### D. Study Procedures

UHCC headache clinic performs 20-25 BoNTA injections a week on average. Enrollment plan is as following: on weekly basis, one of the investigators, either SH or AF, will contact all patients scheduled for BoNTA injections and explain the study's objectives and details. If the subject agrees to enroll, he/she will be assigned a study serial number and will be randomized to one of the two groups. Randomization will be done through a simulated "coin flipper" website; [www.random.org](http://www.random.org). Heads will be assigned to the preserved saline group, and tails will be assigned to the preservative-free saline group. SH and AF will keep the assignment sheet in a password-protected excel file that only they have access to.

On the day of the procedure, informed consent will be confirmed and signed. Then, each subject will receive 10-15 minute session on the appropriate use of headache diary.

Same randomizing investigator will reconstitute BoNTA vial (Allergan Inc) using one of the two identical solutions, and then hand it to the principal investigators; AZ or LM, who will be

performing the procedure using 30G 1/2' needles. AZ ,LM, and the subject will all be blinded to which solution is used for reconstitution.

Following the injections, subjects will be asked to rate procedure-related pain using verbal pain rating scale (0 to 10). They will be asked to maintain a 7-day headache diary (see supplementary). Prepaid mail envelopes will be provided to ensure the return of the diaries following their completion.

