### **III. METHODS**

#### **A. Study Design**

The study is a prospective, randomized, double-blind trial.

Subjects will be enrolled consecutively at UHCC headache clinic from the practice of the two lead authors; AZ and LM who will be performing the injections.

Two of the investigators, SH or AF, will perform the randomization through simulated, web-generated, coin toss.

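### The coin is tossed before consent is signed, and the two investigators who know the result then take that consent

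*Combined protocol and SAP*

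**What the plan says.** Section III.D describes a weekly contact before the visit, at which one of two investigators "will contact all patients scheduled for BoNTA injections and explain the study's objectives and details". Randomization follows from agreement at that contact: "If the subject agrees to enroll, he/she will be assigned a study serial number and will be randomized to one of the two groups". Those two investigators "will keep the assignment sheet in a password-protected excel file that only they have access to". The section then moves to the visit: "On the day of the procedure, informed consent will be confirmed and signed". A diary training session comes next, after which the investigator who randomized the subject reconstitutes the vial. The subject and the two injecting investigators are blinded; the two who randomize are not.

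Section VI.A assigns the taking of consent to the same two investigators, "at the time of the visit. Refusal of participation will not affect the treatment plan". A patient who declines has the scheduled injections with preservative-free saline.

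Section III.C excludes "Subjects whom BoNTA injections deviate from standard protocol for any reason" and follows this with an open-ended list of examples. It does not say who applies the exclusion or when. Section V defines no analysis population and no replacement rule, and does not say how a subject who is randomized but never signs is to be counted.

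**The concern.** Random allocation protects the comparison only if nobody who knows the arm can still affect who enters the trial. Here the arm is known to the consent taker while entry is open. A slight change in how the study is put to a hesitant patient, made knowingly or not, could make signing more likely in one arm than in the other. If the same investigator also applies the Section III.C exclusion, that judgement is exposed in the same way.

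These losses cannot be recovered in the analysis. A subject who does not sign, or who is excluded after the toss, has no pain rating, so there is nothing to analyse as randomized. Replacing such subjects restores the number scored but not the balance between arms.

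The concern is limited in three ways. The first explanation of the study precedes the toss and is unaffected. Each toss is independent and follows agreement, so the next allocation cannot be foreseen. Cancellations started by the blinded subject should fall equally on both arms.

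**Working it through.** **The sequence.** Putting Sections III.A, III.C, III.D and VI.A together:

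| Step | When | Who | Knows the arm? |
|---|---|---|---|
| Study explained, patient agrees | Contact before the visit | One of the two randomizing investigators | No, not yet tossed |
| Coin tossed, result filed | After that agreement | Same two investigators | Yes |
| Consent signed or refused | Day of procedure | Same two investigators | Yes |
| Section III.C exclusion applied | Not stated | Not stated | Yes, if done by those two after the toss |
| Vial reconstituted | Day of procedure | Same randomizing investigator | Yes |
| Injection and pain rating | Day of procedure | Blinded injector and subject | No |

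The gap is between the second and third rows. No other section closes it.

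**The plan's own figure.** Section V gives 70 subjects (35 per group) for a difference of 1.5, SD 1.9, 90% power and alpha .05. A two-sided two-sample t-test needs 34.7 per arm, rounded up to 35, and has 90.2% power at 35. The figure reproduces, and this point does not change it.

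**Size of a possible bias.** From the documents: SD 1.9, 35 per arm, target difference 1.5. Assumed, because the documents give nothing: no true effect; the subjects lost are those ranked highest on a trait correlated rho with pain; the numbers lost in each arm; rho of 0.3 or 0.5.

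If a fraction d of an arm is lost in this way, the mean of those remaining falls by approximately

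rho × SD × φ(z) / (1 − d), where z is the 1 − d quantile of the standard normal distribution and φ its density.

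For 7 of 35 lost, d = 0.20, z = 0.842 and φ(z) = 0.280. With rho 0.5 the shift is 0.5 × 1.9 × 0.280 / 0.80 = 0.33 points. The bias in the comparison is the difference between the two arms' shifts.

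Simulation with exact ranks (100,000 trials per row, pooled two-sided t-test at .05) gives slightly smaller shifts, as expected with only 35 per arm, and supplies the type I error:

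| Lost of 35, arm 1 / arm 2 | rho | Bias (points) | Type I error |
|---|---|---|---|
| 4 / 4 | 0.3 | 0.00 | 5.1% |
| 7 / 7 | 0.5 | 0.00 | 5.7% |
| 2 / 0 | 0.3 | 0.06 | 5.3% |
| 4 / 2 | 0.3 | 0.05 | 5.3% |
| 7 / 4 | 0.5 | 0.12 | 6.4% |
| 4 / 0 | 0.5 | 0.20 | 7.5% |
| 7 / 0 | 0.3 | 0.19 | 7.0% |
| 7 / 0 | 0.5 | 0.32 | 10.6% |

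The 5.7% with equal losses and no bias comes from trimming by rank in the model. A small part of the excess in the other rows has the same source. The last row is 0.32 / 1.5 = 21% of the target difference.

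If lost subjects are replaced until 35 per arm are scored, 4 / 2 at rho 0.3 gives 0.05 points and 5.3%, and 7 / 0 at rho 0.5 gives 0.28 points and just under 10%. Replacement reduces the bias only slightly.

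**The case against.** The strongest reply is that harm needs a chain of events the documents do not establish. Patients who have already agreed must be lost at signature. The loss must depend on the arm through the investigator's conduct. It must also fall on a trait that predicts pain and that the investigator can see. Both arms receive the same toxin in solutions that look alike, and the subject is blinded, so the subject has no reason related to the arm to withdraw. The refusal sentence in Section VI.A reads as a general assurance and does not predict refusals after the toss. The blinded injectors are at least as likely as the randomizing investigators to judge a deviation under Section III.C, and if they do, that route carries no information about the arm. The largest figures need a fifth of one arm lost and none of the other.

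Most of this stands as a limit on likelihood and size. The exclusion route is only conditional, and the extreme case is a bound and should not be read as an expectation. The order of events is not answered, however. Section VI.A has consent obtained at the visit, so the earlier verbal agreement does not make entry final. Blinding of injector and subject protects the injection and the rating, but the person taking consent is unblinded.

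**Conclusion.** The concern holds. On the text, the arm is fixed and known to the consent taker before entry is final. That part is certain. Its effect is not: bias arises only if losses between toss and signature differ by arm in a way related to pain, and the documents give no rates. Under the assumptions above, the effect runs from none, through about 0.05 points with type I error near 5.3% for mild imbalance, to 0.32 points and 10.6% in the extreme case. It may be negligible or material. The point should be fixed because the safeguard costs almost nothing, and not because harm has been shown.

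**What to change.** Reorder Section III.D:

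1. Use the contact before the visit only to inform and pre-screen.
2. Toss the coin at the visit, after consent is signed and the Section III.C exclusions are checked, immediately before the vial is reconstituted.
3. Count the 70 subjects from that toss and analyse all of them as randomized.

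No assignment then exists when consent is signed or when eligibility is judged before injection. A deviation that arises during the injections would still come after the toss, and a subject who leaves after the toss would still have no score. Such cases should be reported by arm.

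The cost is one moved step. The same investigators already attend the visit to take consent and reconstitute, so no staff, visits or subjects are added. If the order in Section III.D is followed, the 10-15 minute diary session between signature and reconstitution leaves time for the toss. The small downside is that the vial cannot be assigned or prepared until consent is signed.

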#### **V. DATA ANALYSIS**

Sample size determination was calculated based on a minimally significant mean difference in verbal pain score of 1.5. To detect this difference with 90% power, alpha = .05; a total of 70 subjects (35 per group) will be required (SD=1.9). T-tests will be used to compare outcome of both groups. Statistical analysis will be carried by GB.

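### Allocation is a web coin toss made by the recruiting investigators, with no prior sequence and consent signed after the arm is known; no rule ties it to 35 per group

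*Combined protocol and SAP*

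**What the plan says.** In section III.A (Study Design) of the combined protocol and SAP, two of the investigators "will perform the randomization through simulated, web-generated, coin toss". Section III.D (Study Procedures) gives the rule: "Heads will be assigned to the preserved saline group, and tails will be assigned to the preservative-free saline group".

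Section III.D also sets the order of events. Each week one of the same two investigators "will contact all patients scheduled for BoNTA injections". Then: "If the subject agrees to enroll, he/she will be assigned a study serial number and will be randomized to one of the two groups". Consent is signed later, on the day of the procedure, and section VI.A (Informed Consent) has it obtained by one of the same two investigators. Only those two can open the assignment file, and whichever of them randomised the subject prepares the vial. The injecting physicians and the subjects are blinded.

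Section V (Data Analysis) bases the sample size on a "minimally significant mean difference in verbal pain score of 1.5". It continues: "To detect this difference with 90% power, alpha = .05", for which "a total of 70 subjects (35 per group) will be required (SD=1.9". The analysis is stated as "T-tests will be used to compare outcome of both groups".

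No section mentions a list prepared in advance, a log or independent check of the tosses, blocking, a limit on either arm, replacement of subjects lost before consent, or a rule for ending recruitment.

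**The concern.** Two gaps meet in the same procedure.

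The first is control of allocation. The person who speaks with the patient then makes the toss, on a website that anyone can use again. With no prior sequence to compare against, a second toss after an unwelcome first result cannot be told from a single honest toss. The arm is then known to that person for the interval between assignment and signed consent. If who signs depends on the arm, the groups compared are no longer the groups the toss created. In a trial of 70 subjects with a self-reported 0 to 10 pain score, such selection could shift the comparison, and an unadjusted t-test would not correct it.

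The second is the missing link between the toss and the group size. An unrestricted toss leaves the split to chance, yet the sample size is stated as 35 in each group. The site would have to decide during recruitment when to stop, with the running totals in front of the people who recruit.

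**Working it through.** **1. Who knows the arm, and when (III.D and VI.A)**

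| Step | Done by | Arm known to that person? |
|---|---|---|
| Weekly contact and verbal agreement | One of the two randomising investigators | No: the toss has not been made, and past independent tosses predict nothing |
| Toss and entry in the file | Same investigator | Yes, from this point |
| Signed consent on the procedure day | One of the same two | Yes: both can open the file |
| Preparation of the vial | The investigator who tossed | Yes, necessarily |
| Injection and pain rating | Blinded physician and blinded subject | No |

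The exposure is at the toss itself and between the toss and the signature. The documents give no rate of loss before consent, so no bias can be calculated.

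**2. The plan's own sample size**

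Inputs from section V: difference 1.5, SD 1.9, alpha 0.05, power 90%. Sidedness is not stated, so two-sided is assumed.

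- Normal approximation: n per group = 2 × (1.960 + 1.282)² × 1.9² / 1.5² = 2 × 10.51 × 3.61 / 2.25 = 33.7, so 34.
- t-test, noncentrality 1.5 / (1.9 × √(1/n₁ + 1/n₂)): power is 89.4% at 34 per group and 90.2% at 35 per group.

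The stated 35 per group is reproduced. A one-sided normal calculation gives 28 and does not reproduce it.

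**3. Splits from 70 independent fair tosses**

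P(exactly 35/35) = C(70,35) / 2⁷⁰ = 9.5%, so the arms are unequal in 90.5% of trials. P(smaller arm ≤ k) = 2 × Σ C(70,j) / 2⁷⁰ for j = 0 to k, with k below 35. Power uses the noncentrality above with 68 degrees of freedom.

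| Split | This unequal or worse | Power |
|---|---|---|
| 35/35 | – | 90.2% |
| 32/38 | 55.0% | 90.0% |
| 31/39 | 40.3% | 89.9% |
| 30/40 | 28.2% | 89.7% |
| 28/42 | 12.0% | 89.1% |
| 27/43 | 7.2% | 88.7% |
| 25/45 | 2.2% | 87.7% |

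Weighting the power at each split by its probability gives an expected power of 89.8%, a loss of about 0.4 percentage points from 90.2%. The mean absolute difference between arms is 6.7 subjects.

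**4. Three ways recruitment might end, none of them stated**

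- Stop at 70: the splits in step 3 apply, and every assignment is random.
- Toss until both arms have at least 35: by simulation of 50,000 trials, the mean total is 76.6 (median 75, 95th percentile 88). Every assignment is random, but the total usually exceeds 70.
- Close an arm when it reaches 35: P(m subjects remain) = 2 × C(69 − m, 34) × 0.5^(70 − m), for m = 1 to 35. The mean is 6.65 (6.65 / 70 = 9.5% of the sample), the median is 6, and P(m ≥ 10) = 24.5%. These subjects would have an arm known before they were approached.

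**The case against.** The strongest reply is that the written procedure does little statistical harm. Simple randomisation is valid, and unequal arms that arise from it are unbiased. At the moment of approach the next arm is unknown even to someone holding the file. Consecutive enrolment and contact with every scheduled patient limit selective approach, and the rating comes from a blinded subject injected by a blinded physician. All of this stands. It does not cover a repeated toss, or a loss between assignment and signature, because both happen after the approach and before the blinded steps.

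Three stronger readings are tempting and are not supported.

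- A reader might infer that the toss and the 35 per group contradict each other. They do not. The 35 is the result of a sample-size calculation with equal arms, not a stated quota. A split of 35/35 can occur by chance, and tossing could continue past 70.
- A reader might infer that the last subjects will be forced into a known arm. No section orders an arm to be closed, so that outcome depends on a choice the site has not been told to make.
- A reader might infer that the trial is underpowered, because 40.3% of trials fall below 90%. That threshold is crossed at 31/39, where power is still 89.9%.

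It is also fair to say that blocks bring a predictability that simple tosses lack. A person who sees past assignments can guess the end of a block. Blocking is an improvement only if the recruiter is kept from that information.

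**Conclusion.** The point holds as a weakness of allocation control, with a missing stopping rule beside it. The same two investigators recruit, toss, record, prepare the vial and take signed consent with the arm known, and nothing in the protocol would reveal a repeated toss or a selective loss. Whether either would occur, and how large the bias would be, cannot be estimated from the documents.

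The group-size part is minor: equal arms are unlikely, but the average power cost is about 0.4 percentage points, assuming fair independent tosses and a two-sided test at the plan's own difference and SD. An advance-known arm for the last 6 to 7 subjects on average arises only if the site chose to close an arm at 35. The sample size itself is sound. This is a cheap improvement that should be made before recruitment, because concealment cannot be restored afterwards; it is not a fatal flaw.

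**What to change.** Amend III.A and III.D as follows.

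- Replace the toss with a 1:1 list of 70 assignments, 35 per arm, in permuted blocks of randomly varying size, generated before the first subject by someone who does not recruit. If the analyst generates it, use coded arms so that the analyst stays blinded.
- Separate the two existing roles. One investigator contacts and consents patients and does not see past assignments. The other receives the assignment and prepares the vial.
- Reveal one assignment at a time, on the procedure day, after consent is signed. A patient who withdraws before signing then uses no place on the list.
- State that enrolment stops at 70 randomised subjects.

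The cost is a short amendment and one generated list, with no extra subjects or staff. The downside is that the two investigators can no longer swap roles freely, and the vial is assigned on the day itself rather than beforehand.
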